8.1 Definitions

This study will use the RECIST 1.1 criteria

Definitions

Response and progression will be evaluated in this study using the international criteria proposed by the Response Evaluation Criteria in Solid Tumors (RECIST 1.1) Committee. Changes in only the largest diameter (unidimensional measurement) of the tumor lesions are used in the RECIST criteria. Measurable lesions are defined as those that can be accurately measured in at least one dimension (longest diameter to be recorded) as >10 mm with CT scan, MRI, or clinically using calipers. The investigator will identify up to 5 measurable lesions to be followed for response. Serial measurements are to be done with CT or MRI. The same method of assessment is to be used to characterize each identified and reported lesion at baseline and during follow-up.

Complete Response: Disappearance of all target lesions

Partial Response (PR): At least a 30% decrease in the sum of the longest diameter (LD) of target lesions, taking as reference the baseline sum LD

Progressive Disease (PD): At least a 20% increase in the sum of the LD of target lesions, taking as reference the smallest sum LD recorded since the treatment started or the appearance of one or more new lesions

Stable Disease (SD): Neither sufficient shrinkage to qualify for PR nor sufficient increase to qualify for PD, taking as reference the smallest sum LD since the treatment started

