4.2.2 Patients with active HIV infection (can be pending at this time)

4.3 Treatment Inclusion Criteria

4.3.1 Any patient with biopsy-proven pancreatic adenocarcinoma:
Group A: Patients with locally advanced or metastatic pancreatic adenocarcinoma who experienced a documented best response of investigator-assessed confirmed PR or SD per RECIST v1.1
Group B: Patients with locally advanced or metastatic pancreatic adenocarcinoma who experienced progressive disease following first line chemotherapy or who are judged by the investigator as being ineligible to receive standard of care chemotherapy
Group C: Patients with potentially resectable pancreatic cancer who have completed planned preoperative neo-adjuvant chemotherapy, radiotherapy or combination chemoradiation

4.3.2 Patients must have measurable or evaluable disease per RECIST 1.1 criteria.

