7.3 Other Studies

- 7.3.1 The following investigations will be obtained at the time points specified in the study calendar:
CBC and differential, BUN, creatinine, bilirubin, SGOT, SGPT, alkaline phosphatase, Na, K, Cl, CO₂, albumin and total protein, and CA19-9.
- 7.3.2 Pregnancy testing (blood) is required on female patients of childbearing potential prior to multiTAA T cell infusion #1.
- 7.3.3 Diagnostic imaging (CT scans, MRI, nuclear imaging) and/or blood tests (serum cytokines) to document measurable disease and response to therapy prior to the first infusion and every 2-3 months thereafter for up to 1 year after the last infusion, as per standard clinical care monitoring for patients with pancreatic cancer. The time may vary by 1-2 weeks due to scheduling issues and may be done earlier if clinically indicated. If diagnostic imaging studies are performed at other times either during or after treatment on this study, that data will be collected and information gained will be used for this study.
- 7.3.4 The following investigations will be obtained at the time points specified in the study calendar. 20-40ml of peripheral blood will be collected in preservative-free heparin.. This blood will be used for analysis of specificity of multiTAA T cell response using HLA multimer analysis and immune function assays including ELIspot, intracellular cytokine staining and cytotoxicity assays. Serum will be batched for analysis of blood cytokine levels. These studies will be done on patients on whom the appropriate reagents are available.
- 7.3.5 Study specific blood tests will cease 12 months after the last T cell infusion but we will continue to follow patients clinically once a year for up to 4 additional years (total of 5 years follow-up) to evaluate long term disease responses.
- 7.3.6 Other Tissues: Should the patient undergo a tumor biopsy/surgical resection at any time while they are on study, a sample of this will be used to assess the tumor antigen expression profile and to look for evidence of T cell infiltration.
- 7.3.7 If a patients' hemoglobin is <7.0g/dl at any of the evaluation times, the amount of blood drawn for the evaluation will be reduced and may be obtained over more than one venipuncture, if necessary.

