10.0 MODIFIED FOLLOW-UP AND OFF STUDY CRITERIA

10.1 Criteria for Modified Follow-Up

The following criteria will result in the patient being ineligible for further treatment on the protocol, although response data will continue to be collected as applicable.

10.1.1 Any patient who develops grade III-IV toxicity related to multiTAA T cells . In such patient the toxicities will be followed until resolution or until their off study date. Although no toxicity has been associated with the infusion of this product in patients with Hodgkin and non-Hodgkin lymphoma or multiple myeloma, we will actively look for evidence of any adverse events, such as cytokine release syndrome.

10.1.2 Any patient who receives any other hematopoietic cell product excluding blood or platelets. In such patients, adverse event data collection will cease.

- 10.1.3 Any patient who experiences Grade 3 or 4 cytokine release syndrome that persists beyond 72 hours. In such patients, the toxicity will be followed until resolution or until their off study date.
- 10.1.4 Any patient whose disease progresses (based on RECIST criteria) and who receives another therapy. In such patients, adverse event data collection will cease.
- 10.1.5 If the patient desires to discontinue treatment or if the physician feels that it is in the best interest of the patient.

Patients who meet modified follow-up criteria remain on long-term follow-up as per the Summary of Monitoring (see table in Section 7.3.1)

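### Section 8.1 names RECIST 1.1 but writes complete response and progression rules that leave out non-target disease, does not say which prevails, and gives patients with evaluable-only disease no workable category

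*Combined protocol and SAP*

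**What the plan says.** All references are to the combined protocol and SAP.

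- **Standard named (8.1).** "This study will use the RECIST 1.1 criteria".
- **Lesions followed (8.1).** The investigator selects up to five measurable lesions. They are measured serially by CT or MRI, with the same method at baseline and follow-up.
- **Complete response (8.1).** "Complete Response: Disappearance of all target lesions".
- **Progression (8.1).** "At least a 20% increase in the sum of the LD of target lesions", relative to the smallest sum since treatment started, "or the appearance of one or more new lesions".
- **Stable disease (8.1).** "Neither sufficient shrinkage to qualify for PR nor sufficient increase to qualify for PD", so it is a residual category of the same target sum. Partial response is a 30% fall in that sum.
- **Eligibility (4.3.2, repeated in the treatment checklist).** "Patients must have measurable or evaluable disease per RECIST 1.1 criteria".
- **Who is assessed (8.0).** Patients with measurable disease are assessed by standard criteria. The same paragraph makes every treated patient who is still enrolled evaluable for response.
- **Use.** Section 2.3 makes PFS a secondary endpoint. Section 9.3.2 reports response rates with exact 95% intervals and PFS by Kaplan-Meier, per group and overall. Section 10.1.4 refers to "Any patient whose disease progresses (based on RECIST criteria) and who receives another therapy".
- **Documentation (7.3.3).** Imaging, including nuclear imaging, "and/or blood tests (serum cytokines) to document measurable disease and response to therapy".

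**The concern.** The written definitions are explicit enough for an assessor to follow and an analyst to program, yet they cover only part of a patient's disease. A sixth lesion, or disease that cannot be measured, enters neither complete response nor progression unless something new appears. Two assessors could classify the same scans differently, one from the named standard and one from the page, and both could claim to follow the protocol.

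The evaluable-only patients raise a second problem. The protocol admits them and counts them as evaluable for response, but every response category is expressed in terms of target lesions that they do not have.

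At stake are the response summaries, the progression times behind PFS, and the application of 10.1.4.

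**Working it through.** The plan gives no figure on this point to reproduce. The check sets the sections side by side and then asks how much one patient can move.

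**1. Target lesions gone, other disease still present.** The complete response rule in 8.1 has one condition, on target lesions, and it is met. No other section adds a condition. The rule as written returns complete response.

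Disappearance of the targets is a 100% fall in their sum, which also exceeds the 30% needed for partial response. If overall response means complete plus partial response (9.3.2 does not define it), this error changes the complete response proportion but not the overall rate.

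**2. Existing non-target disease grows, target sum steady, nothing new.** Neither route to progression is met, so the rule returns stable disease and no PFS event is recorded on that date. If the target sum has fallen by 30% or more, the rule returns partial response. That case does change the overall rate.

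**3. Evaluable-only disease.** There is no target sum, so percentage change has no denominator. Partial response, stable disease and the 20% route to progression cannot be worked out, and complete response has nothing to refer to. Only a new lesion yields a category. Under 8.0 such a patient still counts as evaluable for response.

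**4. Is the missing rule elsewhere?** Section 9.3.2 sends the reader to section 8.4 for response evaluation. The available text of section 8 contains only 8.0 and 8.1, so the reference leads to no rule. The reference list contains no entry for RECIST 1.1.

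**5. Size per patient.** Section 9.1 caps each group at 15 treated patients.

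- One patient moved across a category boundary: 1/15 = 6.7 percentage points.
- Exact (Clopper-Pearson) 95% intervals, the method named in 9.3.2:
  - 0/15 = 0% (0 to 21.8%)
  - 1/15 = 6.7% (0.2 to 31.9%)
  - 2/15 = 13.3% (1.7 to 40.5%)

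**6. Size through the denominator.** The documents do not give the share of evaluable-only patients. Assume 10% to 30%: 0.10 × 15 = 1.5 and 0.30 × 15 = 4.5, so roughly 1 to 5 patients per group. With two responders, also assumed, the rate is 2/15 = 13.3% if everyone is counted. Among measurable patients only, it is 2/14 = 14.3% with one evaluable-only patient and 2/10 = 20.0% with five.

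**7. PFS.** The effect cannot be computed. It depends on how many patients have non-target disease and how often that disease grows first, and the documents give neither.

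**The case against.** The strongest reply is that 8.1 invokes RECIST 1.1 twice and the four definitions read as a summary for target lesions. An assessor who applies the full standard may handle non-target disease properly, and nothing says that the summary replaces the standard. This stands as a limit on the claim. A reader might infer that growth of non-target disease will never count as progression in this trial, but that is true only of the written rules and not necessarily of practice. It does not remove the gap, because the protocol does not say which text prevails. Section 8.1 also describes the criteria as using only changes in largest diameter, which steers the reader towards the narrow rule.

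Four further inferences are tempting and unsupported:

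- **Evaluable-only patients would all be complete responses.** Section 8.0 ties the standard criteria to measurable disease. For the others the category is unassignable, not automatically met.
- **Serum cytokines could establish a response under 7.3.3.** Every category in 8.1 needs lesion measurements from CT or MRI, so a cytokine result cannot produce one. The loose wording in 7.3.3 needs reconciling and no more.
- **Efficacy is biased in a known direction overall.** Cases 1 and 2 favour the treatment, while keeping evaluable-only patients in the denominator lowers the response rate. No net direction is shown.
- **The results could not be compared with other trials that use RECIST 1.1.** The documents do not reproduce the standard, so they cannot support this.

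It is also fair to say that the consequences are limited. Section 9.1 calls efficacy tertiary, and 9.3.2 says that response and survival are not primary. No accrual or stopping guideline uses response or PFS, and overall survival is untouched. Section 10.1.4 requires another therapy as well as progression, and 10.1.5 separately allows the patient or physician to end treatment.

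**Conclusion.** The point holds as a defect in the written response rules. Section 8.1 states rules that, if followed, call complete response with residual disease and ignore growth of existing non-target disease. It does not say whether the named standard overrides them. Patients with evaluable-only disease are admitted and counted but have no workable category apart from progression by a new lesion.

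The response summaries, PFS and the application of 10.1.4 are affected. The primary safety and feasibility endpoints and their monitoring are not. The only size the documents support is 6.7 points per reclassified patient in a group of 15. The 10% to 30% share and the two responders above are assumptions for illustration. If death counts as a PFS event, which I assume because PFS is not defined in detail, many missed progressions would be delayed rather than lost.

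The change should be made because explicit rules feed a secondary endpoint and the remedy is cheap. It does not call the design into question.

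**What to change.** 1. In 8.1, either state that the cited criteria apply in full and prevail over the summary, or amend the definitions. Complete response would then also require disappearance of non-target disease, and progression would also include clear progression of existing non-target disease.
2. Add a rule for patients with evaluable-only disease: include them in PFS, and take the partial response rate from patients with measurable disease. State the denominator of each response rate.
3. Correct the reference in 9.3.2 to section 8.4.
4. Reconcile 7.3.3 with the CT/MRI and same-method requirement already in 8.1.

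The cost is mainly an amendment of wording; no extra scans are needed beyond those 8.1 already implies. Non-target disease must be recorded at baseline. Section 3.6 shows that patients have already been treated, so for them this may need retrospective review of baseline images. Reported complete response and PFS may be slightly less favourable.

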9.0 STATISTICAL CONSIDERATIONS

9.1 Study Design Synopsis

This study is designed as a fixed-dose pilot study to evaluate the safety and feasibility (primary endpoints), and efficacy (tertiary endpoint) of up to 6 intravenous infusion of multiTAA-specific T cells in pancreas cancer patients with metastatic, locally advanced unresectable, or resectable disease.

In each disease group, the sample size is a maximum of 15 patients who receive at least one infusion of multiTAA-specific T cells. The total sample size of the study will be a maximum of 45.

We expect to enroll 15-20 patients per year and therefore expect the study to conclude accrual within the estimated period of 36 months.

Treatment-related serious adverse events (tSAE) are defined as grade III-IV CTCAE toxicity or grade 3-4 CRS toxicities that are determined to be related to T cells.

9.2 Sample Size Determination and Trial Monitoring

In each of the disease groups, the primary goals are to study the safety of multiTAA-specific T cells and determine the feasibility of administering 6 infusions of cells.

To assess the safety of multiTAA-specific T cells: The sample size is 15 patients in each disease group, calculated based on the considerations as follows. To study whether there are excessive treatment-related serious adverse events (tSAE), a tSAE rate of 20% is considered excessive (corresponding to the alternative hypothesis), while a rate below 20% is considered acceptable. Based on our previous experience with T cell therapy, we anticipate at most 1.5% rate (corresponding to the null hypothesis). The monitoring rule is that if more than one tSAE is observed, then the treatment is considered unsafe and the accrual to the trial will be halted for that disease group.

Under the alternative hypothesis that the true tSAE rate is 20%, then the probability of observing more than one tSAE event out of 15 patients is 83.3% (statistical power for rejecting the null hypothesis, based on the exact binomial distribution). Under the null hypothesis that the true tSAE rate is 1.5%, the probability of observing more than one tSAE event out of 15 patients is only 2.08% (type I error for rejecting the null hypothesis, based on the binomial distribution).

There will be no formal interim analysis of safety but we will employ an ad hoc monitoring rule. The cumulative number of treatment-related serious adverse events will be counted for every 3 patients within each group. If there is more than 1 tSAE within a group, then the accrual to that group will be halted for excessive treatment-related serious adverse events. We will be looking at the data for at most 5 times for each group. Under the null hypothesis that the true tSAE rate is 1.5%, the probability of observing more than one tSAE event out of every 3, 6, 9, 12 and 15 patients is 0.07%, 0.32%, 0.76%, 1.34% and 2.08%, respectively. The overall type I error is thus controlled at 4.57% level.

The total sample size is 45. If there is any death deemed possibly or probably related to multiTAA T cell infusion, the study will halt patient accrual for the respective disease group, and the data will undergo a thorough internal review and the outcome discussed with the FDA.

We employ a deterministic rule to assess the feasibility of giving 6 intravenous infusions of multiTAA-specific T cells: In each disease group the feasibility of completing all 6 infusions (henceforth called a series) will be monitored separately using a method similar to the 3+3 procedure. The cumulative number of successful completions of an infusion series will be accounted for every 3 patients. If at most one patient cannot finish the infusion series, then the trial will be allowed to accrue 3 additional patients. If after 6 patients, there are 2 or more patients who are unable to finish the infusion series, then the treatment strategy will be determined to be unfeasible but additional enrollments on that arm will continue.

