2.0 OBJECTIVES

Primary endpoint

- 2.1 To determine the safety of up to 6 intravenous infusions of multiTAA-specific T cells in pancreatic cancer patients with metastatic, locally advanced unresectable, or resectable disease.
- 2.2 To determine the feasibility of completing a total of 6 intravenous infusions of multiTAA-specific T cells to pancreatic cancer patients with metastatic, locally advanced unresectable, or resectable disease.

Secondary endpoint

- 2.3 To evaluate the progression-free and overall survival of patients after multiTAA-specific T cell infusions

Tertiary endpoints

- 2.4 To obtain information on the expansion, persistence and anti-tumor effects of the adoptively-transferred TAA-specific T cells
- 2.5 To determine whether multiTAA-specific T cell infusion enables recruitment of the patients' endogenous immune system as measured by epitope/antigen spreading

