Monitoring: Patients will be monitored for clinical toxicity by the CTEP NCI Common Toxicity Criteria Scale (Version 4.X, See Section 12.3) with the exception of CRS toxicities that are related to T cell infusions. CRS toxicities will be graded according to Appendix I. We will also analyze immunological parameters including T cell frequencies by ELIspot and multimer studies in patients who have HLA types for which multimers are available. Functional analyses (antigen-specific cytotoxicity and cytokine release) will be performed by chromium release assays and ELIspot/intracellular cytokine staining, respectively. The levels of serum cytokines before and following infusion will be compared. A time period of 4 weeks post the 1st infusion will constitute the time for clinical efficacy and safety monitoring. Thereafter patients will receive 5 additional infusions of cells at the same cell dose (or below the patient's original dose can be administered) at monthly intervals. Patients that undergo surgical resections (Group C) will receive 1 infusion prior to surgery and 5 additional infusions of cells at the same cell dose (or below the patient's original dose can be administered) at monthly intervals after surgery.

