8.0 RESPONSE CRITERIA

A 4-week period after the first infusion will constitute a course, which will be evaluated for critical toxicity.

Patients with measurable disease will be assessed by standard criteria to determine clinical response. Evaluations of tumor size will be performed pre-infusion and approx. every 2-3 months thereafter as per standard clinical care patient monitoring. All patients who receive multiTAA T cells and continue to be enrolled on the study will be evaluable for response. Patient long term overall and progression free survival will also be evaluated at 1 year and then annually for up to an additional 4 years (total of 5 years follow-up).

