9.4. Stopping Guidelines

Statistical monitoring of grade III-IV CTCAE toxicity or grade 3-4 CRS toxicities related to T cells is employed. Safety guideline and the rule for halting the accrual will be implemented separately for each cohort. The guidelines serve as a trigger for consultation with the FDA for additional review, and are not formal "stopping rules" that would mandate automatic closure. Additionally, after consultation with the FDA, the PI can stop the study early.

In Group C, it is extremely unlikely that patients who receive their first T cell infusions will not undergo surgical resection since all imaging studies and a clinical plan will be determined prior to infusion and it is unlikely that the T cells will cause inflammation precluding/delaying subsequent surgical resection. The accrual to Cohort C will be halted if any patient experiences a delay in subsequent surgical resection due to toxicity related to the T-cell infusion and this issue will be discussed with the FDA to develop a plan. The plan would be submitted to the DRC and IRB prior to resuming accrual to Cohort C.

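### Sections 10.1.2 and 10.1.4 stop adverse event recording before the 8 weeks that 12.3.3 requires, so a qualifying event can miss the primary tSAE count

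*Combined protocol and SAP*

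**What the plan says.** Objective 2.1 is "To determine the safety of up to 6 intravenous infusions of multiTAA-specific T cells". Section 9.1 gives the event by grade and attribution, with no time limit: "tSAE) are defined as grade III-IV CTCAE toxicity or grade 3-4 CRS toxicities that are determined to be related to T cells". Section 9.2 sets the count, "The cumulative number of treatment-related serious adverse events will be counted for every 3 patients within each group", and halts accrual to a group at more than one event. It calls a 20% rate excessive and says of the other rate: "Based on our previous experience with T cell therapy, we anticipate at most 1.5% rate". Section 9.4 adds: "The guidelines serve as a trigger for consultation with the FDA for additional review, and are not formal" stopping rules that would force closure.

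Recording is governed elsewhere. Section 12.3.3 requires adverse events of any seriousness to be collected until 8 weeks after the last dose. Section 10.1.2 ends collection when a patient receives another hematopoietic cell product other than blood or platelets. Section 10.1.4 ends it when a patient progresses by RECIST and receives another therapy. Neither section refers to the other. Section 12.3.4 sends serious events to an SOP that is not supplied.

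Two sentences describe a shorter period. Section 5.2: "A time period of 4 weeks post the 1st infusion will constitute the time for clinical efficacy and safety monitoring". Section 8.0: "A 4-week period after the first infusion will constitute a course, which will be evaluated for critical toxicity". Section 5.2 continues: "Thereafter patients will receive 5 additional infusions of cells at the same cell dose".

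**The concern.** The safety decision turns on the second event in a group of 15, so one unrecorded event can change it. A patient who progresses and starts another therapy within 8 weeks of the last infusion leaves adverse event recording under 10.1.4 while 12.3.3 still requires it. A related grade 3-4 event that first appears after the switch may then never reach the count. The loss is not random. It falls on patients who progress, and Group B enrols patients who have progressed on first-line chemotherapy or cannot receive standard chemotherapy. It can only lower the chance of crossing the threshold, so it weakens detection of an excessive rate and does not inflate the type I error.

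The 4-week wording in 5.2 and 8.0 adds a smaller ambiguity: someone applying the rule could ask whether events after infusions 2 to 6 count, although objective 2.1 covers up to 6.

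**Working it through.** **The collection rules side by side**

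- 12.3.3: collection to 8 weeks after the last dose, with no exception stated.
- 10.1.2 and 10.1.4: collection ends at the switch. The two rules differ only when the switch falls before week 8.
- 10.1.1: related grade III-IV toxicity is followed to resolution or off-study, but only once it has appeared. It does not capture an event that first arises after a switch.
- 7.1, 7.4 and the end of 10.1: these patients stay on long-term follow-up, with contacts at weeks 4, 6 and 8 after the last infusion. The contact continues while the recording stops.

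**The plan's own figures**

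With n = 15 and more than one event needed, P = 1 − (1−p)^15 − 15p(1−p)^14.

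- p = 0.20: 1 − 0.0352 − 0.1319 = 0.8329 (stated 83.3%).
- p = 0.015: 1 − 0.7972 − 0.1821 = 0.0208 to rounding (stated 2.08%).

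Both reproduce.

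**Size of the loss (illustration)**

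From the plan: 15 patients per group, the 20% rate, monthly infusions in Groups A and B, and 8 weeks of collection after the last dose. Assumed: a month is 4 weeks; the 20% is spread evenly over the full series; the switch comes 4 weeks after the last infusion; m of the 15 patients switch, all after k infusions; the other patients complete the series at 20%.

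1. Window after k infusions: W = 4(k−1) + 8 weeks, so 8, 16 and 28 weeks for k = 1, 3 and 6.
2. Risk with full collection: r = 0.20 × W/28, so 5.71%, 11.43% and 20.00%.
3. Risk captured if cut off: 0.20 × (W−4)/28, so 2.86%, 8.57% and 17.14%. Each patient cut off loses 2.86 percentage points.
4. Power: P0 = (1−r)^m × 0.8^(15−m); P1 = P0 × [m·r/(1−r) + (15−m) × 0.25]; power = 1 − P0 − P1.

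Example, m = 5 and k = 6, cut off: P0 = 0.82857^5 × 0.8^10 = 0.04193; P1 = 0.04193 × (1.0345 + 2.5) = 0.14821; power = 80.99%, against 83.29% with full collection.

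| Patients cut off | Infusions received | Power, full collection | Power, cut off | Fall (points) |
|---|---|---|---|---|
| 3 | 6 | 83.29% | 81.94% | 1.35 |
| 3 | 1 | 75.91% | 74.25% | 1.67 |
| 5 | 6 | 83.29% | 80.99% | 2.30 |
| 5 | 1 | 69.57% | 66.12% | 3.45 |
| 8 | 6 | 83.29% | 79.48% | 3.81 |
| 8 | 1 | 57.63% | 50.35% | 7.28 |

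Falls are taken before rounding. With k = 3 they lie between these values: 1.54, 2.96 and 5.80. Each row compares the same patients under the two collection rules. The lower full-collection figures for k = 1 come from shorter exposure, which no collection rule changes.

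**The case against.** **10.1 is a specific exception to a general rule.** Its heading is modified follow-up, and 10.1.2 and 10.1.4 can be read as modifying 12.3.3. That may settle the wording, but not the loss: the exception is what removes the event from the count.

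**The SOPs may cover it.** Sections 12.3.3 and 12.3.4 both defer to SOPs that are not supplied, and section 11 asks for adverse event records on all patients. This limits certainty that an event would be lost. It does not override explicit protocol text that ends collection. Because 9.1 defines a tSAE by grade, a related grade 3 event that is not otherwise serious need not fall under the SOP for serious events.

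**The consequence is limited.** Section 9.4 makes crossing the threshold a prompt for FDA consultation in a pilot study. That stands and holds down the weight of the point, though a prompt still needs a complete count.

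**Stronger readings that the documents do not support**

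- A reader might infer from 5.2 and 8.0 that only the 4 weeks after infusion 1 count. Section 9.1 has no time limit, 9.2 counts cumulatively, 7.1 schedules contacts after every infusion, and 5.2 goes straight on to the 5 further infusions. The natural reading is that events after any infusion count.
- A reader might give every patient a 20% risk however few infusions they had, and obtain a much larger loss. That contradicts an even risk over time.
- A reader might see a conflict between the long-term adverse event tables in 9.3.1 and the 8-week limit. The long-term follow-up table starts at weeks 4, 6 and 8, inside that limit.

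**Conclusion.** The point holds as an unreconciled collection rule that can remove qualifying events from a primary safety count. Under the stated assumptions, power falls by about 1.3-1.7, 2.3-3.5 or 3.8-7.3 percentage points if 3, 5 or 8 of 15 patients are cut off. These are illustrations: the documents give no rate or timing of switching and no distribution of risk over time. An earlier switch would increase the loss. Risk concentrated soon after each infusion would reduce it.

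The calculation in 9.2 is sound for one event probability per patient. A reader might infer that the type I error is wrong because the 1.5% has no stated period. The documents do not say what exposure or follow-up lies behind that figure, so they neither show an error nor allow a period to be assigned to it. This is a question for the sponsor.

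Weight: minor to moderate, a cheap improvement.

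**What to change.** 1. Reconcile 10.1.2 and 10.1.4 with 12.3.3, so that potential tSAEs (grade 3-4 events assessed for relation to T cells) are still recorded through 8 weeks after the last infusion despite a switch of therapy.
2. State in 9.1/9.2 that the tSAE count runs from the first infusion through that point and covers all infusions.
3. Label the 4-week period in 5.2 and 8.0 as the first course only.
4. Ask the sponsor to confirm what number of infusions and length of follow-up its prior experience, and hence the 1.5%, covers.

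The cost is wording, plus a few more weeks of adverse event recording in patients who switch. No visits are added, because 7.1 already schedules contacts at weeks 4, 6 and 8 after the last infusion. The real downside is attribution: after a switch it is harder to say whether an event is due to the T cells or to the new therapy.

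### Section 9.2 gives the group tSAE halting rule with two different timings; if the every-3-patients count governs, up to two more patients can be infused after the second tSAE, with no saving in type I error

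*Combined protocol and SAP*

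**What the plan says.** Section 9.2 sets "The sample size is 15 patients in each disease group" and contrasts an anticipated tSAE rate of at most 1.5% with an unacceptable one: "a tSAE rate of 20% is considered excessive". It then gives the halting rule in two forms.

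- **General rule.** "The monitoring rule is that if more than one tSAE is observed, then the treatment is considered unsafe", and accrual to that disease group is halted. No counting times are attached.
- **Counting rule.** Introduced as an informal rule in place of a formal interim analysis: "The cumulative number of treatment-related serious adverse events will be counted for every 3 patients within each group". The halting sentence follows: "If there is more than 1 tSAE within a group, then the accrual to that group will be halted". Then comes a cap: "We will be looking at the data for at most 5 times for each group". The per-look probabilities and the overall type I error of 4.57% are calculated for counts at 3, 6, 9, 12 and 15 patients.

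Section 9.4 says that the guidelines prompt consultation with the FDA and do not force closure. It does not say when the count is made.

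**The concern.** The two forms share a threshold but differ in timing. Take tSAEs in patients 3 and 4. Under the general rule, accrual halts before patient 5. Under the counting rule, the count at patient 3 is 1, and the next is due at patient 6, so patients 5 and 6 may enter first. Staff reading 9.2 cannot tell whether patient 5 may be infused.

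Safety is a primary objective (Section 2.0), and this rule is the group-level safeguard for it. A late count also delays the FDA consultation that Section 9.4 ties to the rule. The usual reason for limiting looks is to protect the type I error, so the check is whether the schedule does that here.

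**Working it through.** **Inputs (Section 9.2).** n = 15 per group; limit crossed at 2 or more tSAEs; p = 1.5% (null) and 20% (excessive); counts at 3, 6, 9, 12, 15. **Assumptions.** At most one tSAE per patient, and each patient's outcome known before the next entry.

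**1. The plan's figures.** P(X ≥ 2) = 1 − (1−p)^n − n·p·(1−p)^(n−1).

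- p = 0.20, n = 15: 1 − 0.0352 − 0.1319 = 0.8329. The plan's 83.3% is reproduced.
- p = 0.015, n = 15: 1 − 0.79716 − 0.18209 = 0.02075. The plan's 2.08% is reproduced.
- p = 0.015, n = 3, 6, 9, 12, 15: 0.07%, 0.32%, 0.76%, 1.34%, 2.08%. All are reproduced.

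**2. The 4.57%.** 0.07 + 0.32 + 0.76 + 1.34 + 2.08 = 4.57, so the plan added the five probabilities. The events are nested: the cumulative count cannot fall, so a group above 1 at patient 6 is still above 1 at patient 15 if followed that far. With the same limit at every look, the chance of ever crossing is the chance of crossing by patient 15, which is 2.08%.

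**3. Counting at each event.** The same argument applies with a count after every patient. An exact recursion gives 2.08% at p = 1.5% and 83.3% at p = 20% under both schedules.

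**4. Further patients under the counting rule.** The second tSAE falls in patient n with probability (n−1)·p²·(1−p)^(n−2). Further patients entered = next multiple of 3, minus n. At p = 20%:

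| Second tSAE in patient | Further patients | Probability | Share of crossing groups |
|---|---|---|---|
| 3, 6, 9, 12, 15 | 0 | 0.2911 | 34.9% |
| 2, 5, 8, 11, 14 | 1 | 0.2847 | 34.2% |
| 4, 7, 10, 13 | 2 | 0.2571 | 30.9% |
| Total | | 0.8329 | 100% |

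- At least one further patient: 0.2847 + 0.2571 = 0.5418, or 54% of all groups; 0.5418 / 0.8329 = 65% of crossing groups.
- Mean per crossing group: (0.2847 + 2 × 0.2571) / 0.8329 = 0.96.
- Expected patients entered per group: 9.79 with counts every 3, 8.99 with a count after each patient.
- At p = 1.5%, the chance of any further patient is 1.3%. At assumed rates of 30% and 40% it is 63.1% and 65.0%.

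**5. Accrual stopped before patient 15 (p = 20%).** With counts every 3, the last useful count is at patient 12: P(X ≥ 2, n = 12) = 72.5%. With a count at each event, patient 14 is the last: P(X ≥ 2, n = 14) = 80.2%.

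**The case against.** The strongest reply is that 9.2, read as a whole, already halts at the second tSAE. The general rule has no schedule, and the halting sentence after the counting sentence names no look either. Nothing says that counting happens only at multiples of 3, or that a tSAE seen between counts is to be ignored. On that view the 3-patient count is an extra tabulation. This part stands: a reader might infer that 9.2 literally defers the halt, and the text does not support that. But it does not settle the matter. The cap of five looks is hard to square with a review at every tSAE, and the plan's type I error is built on those five looks. The plan supports both readings and chooses neither.

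Other safeguards exist. A death possibly or probably related to the infusion halts accrual with no look schedule (9.2). A T-cell-related delay of surgery halts Group C (9.4). A patient with a related grade III-IV toxicity gets no further protocol treatment (10.1.1). Serious events are also handled under an SOP and a monitoring plan that are not in these documents (12.3, 14.0), so the speed of action in practice cannot be judged. These limit the harm but do not say when the group count is made.

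Two further inferences fail:

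- **Events after the count at patient 15.** The rule halts accrual, and by then the group is full. No schedule could spare a patient from entry. The judgement that treatment is unsafe is still covered by the general rule.
- **A delay as long as three entries take.** That needs an event arising just after a count in a patient already entered, which is a different timing model from the one behind the 0-to-2 figure. Section 9.1 says only "We expect to enroll 15-20 patients per year" for the whole study and gives no split by group.

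**Conclusion.** The concern holds as an unresolved conflict of timing within Section 9.2. It is not a finding that the plan ignores a second tSAE. If the counting rule governs, the cost is 0 to 2 further patients per group: at a 20% rate, at least one in 65% of crossing groups and a mean of 0.96. At the anticipated rate it is negligible (1.3%). The schedule gives no type I error benefit in return, because the limit is the same at every look.

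These figures rest on outcomes being known before the next entry. The plan states no enrolment pause, and a tSAE can follow any of six infusions, so late events could widen the overshoot under either reading. They also count patients with a tSAE, as the plan's binomial figures do, whereas 9.2 speaks of events.

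**What to change.** Reconcile the two statements in Section 9.2:

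- State that the group's cumulative tSAE count is updated at each tSAE report, and that the existing halt at more than one tSAE applies at that point, in line with the general rule.
- Remove the cap of five looks, and describe the 3-patient counts as summaries.
- Replace the 4.57% overall type I error with 2.08%. The per-look probabilities may stay as descriptive figures, labelled as cumulative and not to be added.

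The cost is a few sentences in 9.2. The threshold, the sample size, the 83.3% power and the 2.08% chance of a false halt do not change. The one downside is that a halt may come 1 or 2 patients earlier than under the 3-patient counts.
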